Screening: Participants who have expressed interest in participating in the study will undergo a brief phone screen to assess eligibility. We plan to phone screen about 2000 participants. If they are eligible according to the phone screen, they will be scheduled for an in-person (or teleconference) study visit. At this visit, a consent form will be reviewed with the study staff. Participants who give permission to receive text messages from the study staff will receive appointment reminders via text two days before upcoming appointments. In addition, subjects will be instructed on how to use our phone app for tracking their medical marijuana use, they will fill out some questionnaires and also do a urine drug and if applicable, a pregnancy test. Also at this visit, participants will be randomized to either the active study group or the waitlist control group. We plan to randomize 200 participants to each group.

Study Design: The active study group will be asked to call the study staff once they receive their MM cards. A staff member will follow up via phone with participants who do not contact study staff within approximately two weeks after the screening visit. Staff will contact participants again after approximately four weeks and six weeks to check in on the status of the medical marijuana card application. If after six weeks, a participant still has not made any progress on the application for a

medical marijuana card (i.e., made an appointment with a doctor who recommends medical marijuana), the participant will be discontinued from the study and a three-month follow-up visit will be scheduled.

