When participants in the active study group receive their medical marijuana card, they will be scheduled for a baseline assessment in which they will undergo cognitive testing, interviews, questionnaires, and possibly an MRI scan (see Measures below). In contrast, participants in the waitlist control group will be scheduled for the baseline visit approximately 3-4 weeks following the screening visit. All participants will then be scheduled for repeat assessments at approximately 2 weeks, 1 month, 3 months, 6 months and 1 year after the baseline visit. All participants will receive monthly check in phone calls from a research coordinator at approximately 2, 4, 5, 7-11 months past baseline in order to update study staff on medication changes, recent substance use, and overall physical and mental health. Participants will also be asked to complete a 2-year follow-up phone call, which is identical to previous check in calls, with the addition of the CGI and CUD checklist. If participants are in the active study group, we will ask that they not use MM on the day of testing (though they can use it after testing on that day). These visits will take approximately 3 hours to complete.

In consultation with their prescribing physician, participants in the waitlist control group will be asked to wait to start using MM until they have completed Visit 5 (Three Months). During those 3 months, they will be assessed at the same time points as those in the active MM group (see study schema). After the 3-month waitlist period, the waitlist control group will have the option to start using MM. If this group fails to adhere to the waitlist control, they will be kept in the study and will be asked to complete the same assessment schedule as those initially assigned to the active study group. All participants will be assessed after 1 year.

Measure	Instrument	Visit 1	Visit 2	Visit 3	Visit 4	Visit 5	Visit 6	Visit 7
		Screen	Baseline	Two Weeks	One Month	Three Months	Six Months	One Year
General Medical/Psychiatric Health								
Medical History/ CON MEDS		x	x	x	x	x	x	x
Quantitative cannabinoids			x	x	x	x	x	x
Drug Screen/pregnancy		x	x	x	x	x	x	x
Psychiatric Interview	MINI 7 + Past SUD and AUD	x						x
Suicidality and Health Risk Taking	CHRT	x	x	x	x	x	x	x
Emotional and physical Functioning	SF-12		x	x	x	x	x	x
ADHD symptoms	ASRS		x					x
Impulsivity	BIS-11		x			x	x	x
Executive function	BRIEF		x			x	x	x
Risk perceptions and behavior	DOSPERT		x			x		

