MRI Protocol (Optional): The purpose of the MRI portion of the study is to investigate possible changes in the brain from those who obtain MM cards. Therefore, only patients randomized the active MM group will be given the option to undergo a 3T MRI scanning. Participants will undergo MRI scanning at baseline and at 1 year after initiation of MM. In addition, a small group (n = 25) of non-MJ-using controls, matched on demographics, will also be scanned at baseline and after 1 year in order to allow us to assess normative change over time. Each scan session will last up to two hours during which structural and functional data will be collected. Participants will be positioned in the scanner and outfitted with audio and visual presentation and response indicator equipment. Visual images and auditory stimuli will be presented using MRI compatible presentation software and hardware. Participant responses are monitored using MRI-compatible keypads, and reaction times may be recorded for subsequent analysis of timing and accuracy of task performance.

Participants may undergo the scans noted below:

1. Structural MRI

For the structural imaging sessions T1 -weighted sequences may be acquired. Multiple anatomical imaging sequences may be run to assess specific image quality measures. The same anatomical scans will be repeated varying a limited range of pulse sequence parameters to assess their effect on the image contrast, image artifacts and signal to noise ratio. Parameters that will be varied may include the repetition time of the MR acquisition (TR), the echo time of the acquisition (TE), and the presence of pre-acquisition inversion pulses. The above parameters will also be evaluated in pulse sequences, which acquire parameters used in the reconstruction of the MR images. The software and hardware interlocks put in place by the scanner manufacturer ensure that the range of these parameters will be maintained within the FDA's non-significant risk criteria.

2. Functional Magnetic Resonance (fMRI)

The scanner is outfitted with audio and visual presentation and response indicator equipment. All tasks are programmed using presentation software that is synchronized with the video

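### Nothing places the active arm's Visit 2 before first medical marijuana (MM) use, yet it is the only baseline for SF-12, CANTAB and MRI

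*Combined protocol and SAP*

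**What the plan says.** Allocation comes first. Under V. Study Procedures, Medical Marijuana Participants, Screening: "Also at this visit, participants will be randomized to either the active study group or the waitlist control group".

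The two arms then reach Visit 2 by different routes (Study Design, same section):

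- **Active arm:** "The active study group will be asked to call the study staff once they receive their MM cards". Staff otherwise check by telephone at about two, four and six weeks after screening. The visit follows the card: "When participants in the active study group receive their medical marijuana card, they will be scheduled for a baseline assessment".
- **Waitlist arm:** "participants in the waitlist control group will be scheduled for the baseline visit approximately 3-4 weeks following the screening visit".

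The rules on use also differ. For the waitlist arm, "participants in the waitlist control group will be asked to wait to start using MM until they have completed Visit 5 (Three Months"). For the active arm the only request concerns the test day itself: "we will ask that they not use MM on the day of testing (though they can use it after testing on that day").

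In the schedule of measures, the SF-12 row ("Emotional and physical Functioning"), the CANTAB row and all three MRI rows are blank at Visit 1 and first marked at Visit 2. The CUD checklist, BPI, AIS and HADS are marked at both visits.

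MRI Protocol (Optional) states: "Participants will undergo MRI scanning at baseline and at 1 year after initiation of MM". Study Design instead counts the one-year assessment from the baseline visit.

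The Summary of Changes lists SF-12 and cognition (baseline to 12 weeks) and brain-based measures (baseline to 1 year) as the secondary outcomes.

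**The concern.** A baseline should be measured before the assigned exposure can act. Here the trigger for the active arm's baseline is the event that gives access to MM. A participant may use it on any day between card receipt and the day before Visit 2 and still comply with everything the plan asks. The waitlist arm has no corresponding route, so any exposure captured at Visit 2 is post-randomization and falls in one arm.

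For the four primary instruments a Visit 1 value exists to fall back on. For SF-12, CANTAB and MRI there is none. If part of the effect is already present at Visit 2, it is treated as the starting level and removed from the estimated effect. Aim 2 looks for cognitive and psychiatric harm and Aim 3 for change in neurocircuitry, so an understated effect could be read as reassurance.

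**Working it through.** The plan gives no figure on this point to reproduce. The check has two parts: a reading of the schedule, then the size of the effect under stated assumptions.

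**1. Schedule.** Instruments with a Visit 1 value:

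- Primary outcomes: CUD checklist, HADS, BPI, AIS, that is 4 of 4.
- Secondary outcome families: SF-12, CANTAB, MRI, that is 0 of 3. The WTAR is taken at Visit 1, but it measures intelligence and reading, not a listed cognitive outcome.

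**2. Rules linking Visit 2 to first use.** There is no maximum interval from card to visit, no statement that Visit 2 comes before first use, and no rule for handling a baseline taken after it. A card that arrives just after one staff call and is not reported would come to light at the next call, about two weeks later, with booking time on top. The interval from Visit 2 to the first follow-up is itself about two weeks.

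**3. Attenuation.** Let D be the effect at follow-up, taken as the same whether or not a participant started early. Let f be the share of the active arm who started before Visit 2, s the share of D already present then, and b the coefficient on baseline. Assume no shift in the waitlist arm.

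- Shift in the active-arm baseline mean: f*s*D.
- Estimated effect: D - b*f*s*D = D(1 - b*f*s).

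The documents give no value for f, s or b. On b, the protocol body (Data Analysis Plan, item a) tests condition by time on baseline and 3 months. With two time points that is a comparison of changes, so b = 1. The Summary of Changes replaces this with adjustment for baseline, where b is estimated from the data. Fraction of the effect retained:

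| f | s | b = 1 | b = 0.5 |
|---|---|---|---|
| 0.10 | 0.5 | 0.950 | 0.975 |
| 0.25 | 0.5 | 0.875 | 0.9375 |
| 0.50 | 0.5 | 0.750 | 0.875 |
| 0.50 | 1 | 0.500 | 0.750 |

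For example, at f = 0.25 and s = 0.5, 1 - 1*0.25*0.5 = 0.875, a loss of 12.5%. With b = 0.5, 1 - 0.5*0.25*0.5 = 0.9375, a loss of 6.25%.

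**4. Effect on power, for scale only.** Take a contrast assumed to have 80% power at two-sided 5%. Retaining a fraction r of the effect gives power Φ(r*(1.960 + 0.842) - 1.960).

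- r = 0.875: Φ(2.452 - 1.960) = Φ(0.492), about 69%.
- r = 0.9375: Φ(2.627 - 1.960) = Φ(0.667), about 75%.

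**The case against.** **Exposure before Visit 2 is recorded.** TLFB, urine screening and quantitative cannabinoids are scheduled at Visit 2, and daily diaries run from Visit 1, with paid entries for up to five weeks before baseline. This stands, and it makes the problem largely identifiable. But no analysis rule uses these data for the purpose.

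**The baseline is not cannabis-free anyway.** Only daily use is excluded at entry. That is true, but prior use precedes randomization and is expected to balance between arms. Use after card receipt is the assigned exposure and arises in one arm.

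**Same-day abstinence serves Aim 2**, which concerns cognition when not acutely intoxicated. It does serve that aim, but it does not address use on earlier days.

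The documents do not support several stronger readings that a reader might infer:

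- *The effect shrinks by f itself (10% at f = 0.10, 25% at f = 0.25).* This needs a change score and the full effect already present at Visit 2. The constant effect in the Summary of Changes is assumed over the follow-up visits at 2 weeks, 1 month and 3 months, not over the days after card receipt.
- *MRI is affected most.* The Analytic Plan models imaging with individual intercepts and slopes. If change accrues at a steady k per week, a start two weeks before the scan gives 2k at Visit 2 and 54k 52 weeks later. The change is 52k, as it would be with a start at Visit 2. There is also a group of 25 controls scanned at baseline and one year.
- *The bias must be towards no effect.* That requires early and later effects of the same sign. The SF-12 is also not specifically a harm measure.
- *Visit 2 should be tied to the certification appointment.* All follow-up is timed from Visit 2, so early follow-up visits could then fall before first use. The Summary of Changes also reports that many participants never obtained a card, so such baseline visits could often be wasted.

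**Conclusion.** The point holds as a gap in the design of the secondary outcomes. The plan as written allows post-randomization exposure, in the active arm only, to enter the sole baseline for SF-12, CANTAB and MRI.

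The documents do not show that it happened or how often. At the assumed f = 0.25 and s = 0.5, the loss is 12.5% for a change score and about 6% with b = 0.5. It is smaller if few started early, and larger if many did and effects appear quickly. Attenuation assumes that early and later effects share a sign and that an early start does not raise the effect at follow-up. No one of the three outcomes is shown to be worse affected than the others. The primary instruments are outside this point because each has a Visit 1 value.

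**What to change.** 1. Add the SF-12 to the Visit 1 questionnaires, completed before allocation is revealed, and use that value as the SF-12 baseline. This helps participants screened after the change. CANTAB and MRI would still rely on Visit 2.
2. Record the card date and the first-use date. Using the TLFB, diaries and urine results already collected, flag every active participant who used MM between card receipt and Visit 2. A positive urine result alone is not enough, because non-daily use is allowed at entry; the dated records are needed. Specify in advance a sensitivity analysis of SF-12, CANTAB and MRI change without those participants. The exclusion is made after randomization and in one arm, so the result is supportive only. Where the main analysis of an outcome has already been run, label the addition post hoc.
3. Reconcile MRI Protocol (Optional), which times the second scan from MM initiation, with Study Design, which times it from the baseline visit. State which date anchors the one-year assessment.

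The cost is about two minutes at Visit 1 and a little more analysis work. None of this changes when Visit 2 is held or sets any rule on MM use.

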dose/frequency, type of maintenance medication use (e.g. reduction/discontinuation in opiate use) also with real time, daily diaries. We will also examine whether or not MM patients experience loss of control over intake of marijuana or other substances. We will use measures such as development of tolerance, escalation of use, marijuana caving, and assess experience of reinforcing effects (e.g. euphoria or 'high'), and withdrawal among those who choose to stop using marijuana.

Any changes throughout 12 months in perception of disease symptomatology or in use of maintenance medication will be compared to the waitlist control group.

Aim 2: To assess neurocognitive and psychiatric effects of MM. We expect that neurocognitive outcomes, such as working memory, attention, executive function, anhedonia, amotivation, and decision-making, (when not acutely intoxicated) may be worsened with MM use. Outcomes may be worse in those who use more frequently/heavily (as measured by quantitative THC screens and dosing dairies).

Aim 3: In a subset of patients, assess how MM effects neurocircuitry of prefrontal function. We will use functional MRI tasks to assess working memory, inhibitory control, sustained attention, and risk/reward task performance and brain activation patterns. We expect that individuals who use MM may experience changes from baseline in neurocircuitry involved in memory, attention, inhibitory control and reward.

Aim 4: To assess how medical marijuana patients compare to healthy controls in structural and functional brain imaging measures. We will use functional MRI tasks to assess memory, inhibitory control, sustained attention, and risk/reward task performance and brain activation patterns. We expect that individuals who use MM to show alterations in task-related brain activity.

III. PARTICIPANT SELECTION

Medical Marijuana Participants

Inclusion Criteria:

1. Men and women aged 18-65 years, inclusive;
2. Competent and willing to provide written informed consent;
3. Desire to use medical marijuana for self-reported pain, sleep, or affective (mood and/or anxiety including PTSD) symptoms.
4. Not in possession of a medical marijuana card, but expressing intent to get one.
5. Able to communicate in English language.

Exclusion Criteria:

1. Current daily marijuana use (prior to enrollment)

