For the structural imaging sessions T1 -weighted sequences may be acquired. Multiple anatomical imaging sequences may be run to assess specific image quality measures. The same anatomical scans will be repeated varying a limited range of pulse sequence parameters to assess their effect on the image contrast, image artifacts and signal to noise ratio. Parameters that will be varied may include the repetition time of the MR acquisition (TR), the echo time of the acquisition (TE), and the presence of pre-acquisition inversion pulses. The above parameters will also be evaluated in pulse sequences which acquire parameters used in the reconstruction of the MR images. The software and hardware interlocks put in place by the scanner manufacturer ensures that the range of these parameters will be maintained within the FDA's non-significant risk criteria.

2. Functional Magnetic Resonance (fMRI)

The scanner is outfitted with audio and visual presentation and response indicator equipment. All tasks are programmed using presentation software that is synchronized with the video synch pulse of the computer running the task. The presentation software also collects the behavioral response information. The experimental paradigms will assess activation in brain regions underlying memory, attention, inhibitory control, and risk/reward. Participants may earn points for correct answers, and those points may be converted to monetary values. The experimental paradigm will take approximately 45 minutes to complete. We will also assess resting-state functional connectivity using standard FC-MRI sequences. The entire scan will last about one hour.

Drug Testing: At both study visits, participants will provide a urine sample, which will be used to qualitatively screen for cannabis use as well as other substances of abuse. An alcohol reading may also be taken if there is any concern about a participant being intoxicated.

Medical Marijuana Participants

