synch pulse of the computer running the task. The presentation software also collects the behavioral response information. The experimental paradigms will assess activation in brain regions underlying memory, attention, inhibitory control, and risk/reward. Participants may earn points for correct answers, and those points may be converted to monetary values. The experimental paradigm will take approximately 45 minutes to complete. We will also assess resting-state functional connectivity using standard FC-MRI sequences. The entire scan will last about one hour.

V. REMUNERATION

Healthy Control Participants

Participants in the healthy control group will be paid for the completion of each study visit. Each study visit is compensated in the amount of \$50. If participants undergo the screening visit but are not eligible, they will be paid \$20 for the first visit only. There are opportunities to receive additional money in the MRI scanner (\$1- \$50) based on scan task performance. All participants who drive to visits will also be given parking vouchers for each visit. This level of compensation is deemed appropriate given the time commitment. All payments will be made via check following each study visit.

Medical Marijuana Participants

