Participants in the medical marijuana study will be paid after the completion of each study visit, and weekly for submitting their dosing diaries. Participants will be compensated \$20 on the day of the screen and \$60 for each study visit. Participants will be paid an additional \$40 after completing their six month visit and an additional \$60 after completing their twelve month visit. Participants will be paid \$10 for completing seven monthly 10-minute check in phone calls at months two, four, seven, eight, nine, ten and eleven with a research coordinator. The purpose of these phone calls is to record AEs, medication changes, TLFB, and symptom severity (measured by the SF-12). Participants will be paid an additional \$5 for completing the EPII and \$5 for completing the Covid19-CSU. If participants undergo the screening visit but are not eligible, they will be paid \$20 for the first visit only. They will be paid \$20 per week for submitting dosing diaries during the first three months of the study, for a maximum total of \$260 for completing all dosing diaries. Additionally, they may be paid for pre-baseline daily diary entries for a maximum of five weeks (\$20 per week, \$100 total). They will be paid \$50 for each scan if they agree to undergo scanning procedures. For each scan participants may also receive additional money (\$1-100) based on scan task performance. All participants who drive to visits will also be given parking vouchers for each visit. All payments will be made via check at the end of the study.

Please see table below for payment schedule.

Visit #	Active Study Group	Waitlist Control Group
1	Screening	\$20
2	Baseline	\$60
3	2 weeks	\$60
4	1 month	\$60
5	3 months	\$60
	Dosing Diaries (13 weeks x \$20/week)	\$260
6	6 months	\$100

	Monthly phone calls 2, 4, 7-11 months (7 x \$10 each)	\$70	Monthly phone calls 2, 4, 7-11 months (7 x \$10 each)	\$70
	Covid19 Questionnaires	\$10	Covid19 Questionnaires	\$10
12	12 months	\$120	12 months	\$120
Total		\$820	Total	\$820
Scan (Optional)	Baseline	\$50		
	12 months	\$50		
Total		\$920		

VI. PARTICIPANT ENROLLMENT

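### Scan-task winnings run to $50 for healthy controls but $100 per scan for marijuana patients, so the payment schedule differs by group in Aim 4's risk/reward comparison

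*Combined protocol and SAP*

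**What the plan says.** The two payment rules are in Section V, Remuneration.

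- Healthy controls: "There are opportunities to receive additional money in the MRI scanner", in a range of $1 to $50 that depends on task performance. The fixed payment is stated as "Each study visit is compensated in the amount of \$50", and the MRI is their second visit.
- Medical marijuana participants: "For each scan participants may also receive additional money (\$1-100) based on scan task performance". The fixed payment is "They will be paid \$50 for each scan if they agree to undergo scanning procedures".

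The fMRI paragraph in Section V, Study Procedures, appears once for controls and once for patients with the same description of the task domains. Both versions contain the sentence "Participants may earn points for correct answers, and those points may be converted to monetary values". Neither gives a rate.

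Section II, Aim 4, compares medical marijuana patients with healthy controls using "functional MRI tasks to assess memory, inhibitory control, sustained attention, and risk/reward task performance and brain activation patterns".

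The Data Analysis Plan, part (c) Imaging Data, fits a linear mixed-effects model for each region or voxel. It does not mention incentive size or the payment difference.

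**The concern.** In a task scored for money, the money on offer is part of the experimental condition. The plan itself pays on performance. If one group plays for more than the other, a difference in reward-task performance or activation may reflect the payment rule as well as the group. The distortion could run either way: it could create a group difference, or it could hide a deficit in the better-paid group.

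As written, every scanned patient is under one range and every control is under the other. Only patients randomised to the active arm are offered scanning, so no patients are on the control schedule who could serve as a bridge. The protocol introduces this difference between the groups itself, gives no reason for it, and could remove it.

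**Working it through.** **Inputs from the documents**

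| Item | Healthy controls | Marijuana patients |
|---|---|---|
| Fixed payment for the scan | $50 (visit) | $50 (scan) |
| Minimum winnings | $1 | $1 |
| Maximum winnings | $50, basis not stated | $100 for each scan |
| Points-to-money rate | not given | not given |
| Paradigm description | same wording | same wording |

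The fixed payment and the floor agree. The gap lies only in the part that depends on performance.

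**Can the payment table settle it?** For patients, 20 + 4 × 60 + 260 + 100 + 70 + 10 + 120 = 820, and 820 + 2 × 50 = 920. Both printed totals reproduce. Neither includes winnings, so the table does not show which range was intended.

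**Ratio of the upper limits**

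- Control range read as per scan: 100 / 50 = 2.
- Control range read as a total over two scans: (2 × 100) / 50 = 4. This reading is an assumption. The MRI Protocol (Optional) paragraph has 25 controls scanned at baseline and after 1 year, whereas the controls' own schedule table shows one MRI visit.

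**What the ranges imply for the incentive.** This depends on the missing rate. On the per-scan reading there are three cases.

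1. Same rate, and controls rarely reach $50. Each point is worth the same in both groups and the incentive is effectively equal.
2. Same rate, and controls do reach $50. The incentive is equal up to that limit; beyond it, further points are worth nothing to a control but still pay a patient.
3. Rate scaled so that the same best score earns each group's maximum. From floor to ceiling, a point is worth (100 − 1) / (50 − 1) = 99 / 49 ≈ 2.0 times as much to a patient.

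**Can the model separate incentive from group?** In case 3 the rate takes one value for all patients and another for all controls. It is then a linear function of the group indicator, and its own coefficient cannot be estimated beside group. In cases 1 and 2 winnings vary within each group and can overlap between groups. They are a result of task performance, however, so entering them as a covariate would adjust for part of the outcome.

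**Reach.** Structural and resting-state measures involve no task payment. For patients the stated range is the same at both scans, so within-patient change (Aim 3) is not affected. The randomised comparison and its cannabis use disorder, pain, sleep, depression and anxiety outcomes do not use the scan tasks.

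**The case against.** A range of possible winnings is not a stake. A reader might infer from $100 against $50 that patients play for twice as much. The documents do not support that: they give no rate, no reward per trial and no expected winnings. The ranges overlap over the whole of $1 to $50, nothing shows that $50 was a limit controls actually met, and one figure may be a budget allowance or a drafting slip. This objection stands. It means the confounding is conditional, and inseparability of incentive and group is established only if the conversion rule itself differs.

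A reader might also want a false-positive rate for the group contrast. That would need a shift in the reward contrast due to payment and the number of scanned patients, and neither is in the documents. Any such figure would simply be the power of a test against an effect chosen by the person calculating it, so none is given here.

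It can further be said that Aim 4 is non-randomised and that its groups already differ on illness, medication, psychiatric diagnosis and past marijuana use, so it could not isolate marijuana in any case. That is true and limits the importance of the point. It does not excuse adding a removable difference to a comparison whose controls are to be demographically matched.

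Finally, a change in the middle of the study can do harm. Lowering the patient range after baseline scans would give the same person different incentives at baseline and 1 year, and would spoil a within-patient comparison that is now clean. The fix below allows for this.

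**Conclusion.** The point holds in a limited form. As written, the performance-payment schedule differs systematically between the two groups that Aim 4 compares on risk/reward tasks, with no stated reason and no provision in the analysis. The upper limits differ 2:1 if the control range is per scan, or 4:1 over two scans if it is a total. The size of any bias cannot be computed. It could be nil under a common rate with a limit that seldom binds; under different rates, incentive size and group could not be separated. The point also assumes that the money on offer can influence an incentive-linked task.

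The consequence is confined to incentive-linked tasks in the non-randomised Aim 4 contrast. It would be wrong to read it as a threat to the trial's imaging results in general or to its randomised outcomes. It is worth correcting because the correction is specific and cheap.

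**What to change.** Reconcile the two Remuneration paragraphs. State one points-to-money rule and one maximum per scan for both groups, and keep each patient's rule the same at baseline and 1 year. Aligning the control range to the patient range does this without touching the patients' schedule.

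Cost: a sentence of text, plus at most 100 − 50 = $50 per control scan if the control range is per scan, so 25 × 50 = $1,250 per round. If the control range was meant as a total over two scans, the most it could add is 25 × (200 − 50) = $3,750 over both rounds.

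If scans have already been done, check the conversion rule that was programmed and the recorded winnings before changing the analysis.

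- If the rule was common and controls rarely met the $50 limit, say so and correct the text.
- If the rule differed, do not attribute a risk/reward group difference to marijuana or illness, and keep that task for within-patient change.
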